#### **2.2.3. Definition of subgroups**

The main efficacy indicators will undergo subgroup analysis based on the following subgroups.

Table 2.2.3-1 Subgroups in the study

Subgroup	Definition
Sex	

• Male

• Female

Age grouping	

• <65 years old

• <math>\geq 65</math> years old

Baseline brain metastasis status	

• Present

• None

History of smoking	

• Yes

• None

EGFR gene mutation type	

• Ex19del

• L858R

Baseline ECOG PS score	

• 0

• 1

#### 2.2.4. Random stratification error

If a stratifying factor entered into the IWRS randomization system is inconsistent with the actual stratification information during the screening period, the inconsistent information should be recorded and listed. Subjects receive treatment in accordance with their existing randomized grouping results. Subjects' actual stratification information during the screening period is used for statistical analysis.

#### 2.2.5. Study date and relative date of visit

For the summarization of effectiveness data, the first day of the study is defined as the date of randomization. If the date of the visit (or event) occurs on or after the date of randomization, the number of days of the study is defined as the date of the visit (or event) - the date of randomization + 1; if the date of the visit is before the date of randomization, the number of days of the study is defined as the date of the visit (or event) - the date of randomization.

For the summarization of safety data, the first day of the study is defined as the date of first medication. If the date of the visit (or event) occurs on or after the date of first medication, the number of days of the study is defined as the date of the visit (or event) - the date of first medication + 1; if the date of the visit is before the date of first medication, the number of days of the study is defined as the date of the visit (or event) - the date of first medication.

#### 2.2.6. Analysis visit window

Subjects may not undergo visits on the dates stipulated by the protocol for various reasons during the trial. Therefore, during analysis, it is necessary to designate the corresponding analysis visits for the observation values of different indicators during each visit based on the examination dates.

Safety data such as vital signs, laboratory testing, ECG, LVEF, ECOG, and physical examinations will be analyzed during the analysis visits defined in [Table 2.2.6-1](#) (analysis visits determined based on subjects' first medication dates and actual examination dates). The upper limit of the analysis visit window after C1D1 will be set based on the sum of half of the difference between the scheduled study date of the visit and the number of days from adjacent visits.

The summary analysis by visit follows the following rules:

- 1) If a subject has 2 or more visit records during the same visit window as defined above, the results recorded from the visit closer to the planned study date serve as the assessment values for the visit window. The other visits will not be analyzed in the summary table. If two visits are the same distance from the planned study date of the visit window, the earlier visit is used for the evaluation in the visit window.
- 2) For summarization at the individual level, all data of the subject should be included in the analysis, regardless of whether the measurement is from a planned visit or an unplanned visit, including the maximum values of statistics derived on the individual level.

The visit data of the subjects at all time points will be presented as a list.

Table 2.2.6-1 Definition of analysis visit window

Serial number	Analysis visit name	Scheduled study date	Lower limit of the window	Upper limit of the window
1	Screening period	1	-28	1
2	C1D8	8	2	11
3	C1D15	15	12	18
4	C2D1	22	19	32
5	C3D1	43	33	53
6	C4D1	64	54	74
7	C5D1	85	75	95
8	C6D1	106	96	116
9	C7D1	127	117	148
10	C9D1	169	149	190
11	C11D1	211	191	232
12	C13D1	253	233	274
13	C15D1	295	275	316
14	C17D1	337	317	358
15	C19D1	379	359	400
16	C21D1	421	401	442

17	C23D1	463	443	484
18	C25D1	505	485	526
19	C27D1	547	527	568
20	C29D1	589	569	610
21	C31D1	631	611	652
22	C33D1	673	653	694
23	C35D1	715	695	736

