10.1.12 Echocardiography

Echocardiography will be performed to assess the patient's LVEF every 12 weeks from the first dose of the investigational product as per the study plan ([Appendix B](#)).

One subject should be examined using the same machine and operator whenever possible during the course of the study.

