##### **1.2.2.2.2. Treatment visit (C1-C7+, D1-D127+)**

**Treatment visit (C1-C7, D1-D127)**

Treatment period visits are performed on the first day (CnD1, N = 1-7) of the first 7 cycles of treatment (C1-C7). During the first cycle, in addition to C1D1, two visits are added on C1D8 and C1D15. The specific visit process follows:

- Administered once a day
- Comprehensive physical examinations, body weight checks, ECOG PS scoring, vital sign checks, laboratory testing (clinical biochemistry, hematology, and urine testing), and 12-lead ECGs are performed once every 3 weeks (CnD1)
- Two examinations are added on C1D8 and C1D15: Including vital sign checks, laboratory testing (clinical biochemistry, hematology, and urine testing), and 12-lead ECGs
- Throughout the treatment period, ophthalmological examinations are performed as clinically needed. The examination items are determined by the investigator or specialist based on the patient's condition
- Echocardiography is performed once every 12 weeks (and as clinically needed) from the first administration
- Solid tumor efficacy evaluation is performed once every 6 weeks according to RECIST 1.1
- Record adverse events and concomitant medications

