#### **5.6. LVEF measured with echocardiography or MUGA**

The following will be summarized by treatment group at each visit and after treatment:

- Summary of the proportion of subjects with LVEF value  $<$  50% and decrease versus baseline  $\geq$  10%
- Summary of the proportion of subjects with LVEF value  $\geq$  50% and decrease versus baseline  $\geq$  15%.

All LVEF results of each subject will be presented by list.

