14.3.5 LVEF	Table 14.3.5.1 Summary of LVEF abnormalities by visit-safety set Table 14.3.5.2 Summary of LVEF abnormalities after treatment-safety set
14.3.6 Physical examination	Table 14.3.6.1 Cross table of physical examination results before and after treatment-safety set Table 14.3.6.2 Summary of normal or abnormal [tests] without clinical significance at baseline that turned to abnormal with clinical significance after treatment (physical examination)-safety set

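### LVEF is tabulated in visit windows 1 to 6 weeks apart although echocardiography is due every 12 weeks, so 14 of the 22 post-baseline windows contain no scheduled scan

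*SAP*

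**What the plan says.** SAP 2.2.6 uses one set of windows for every safety measure and names LVEF among them: "Safety data such as vital signs, laboratory testing, ECG, LVEF, ECOG, and physical examinations will be analyzed during the analysis visits defined in" Table 2.2.6-1. A scan is placed by date, with "analysis visits determined based on subjects' first medication dates and actual examination dates", and SAP 2.2.5 sets the origin: "For the summarization of safety data, the first day of the study is defined as the date of first medication". The table ("Table 2.2.6-1 Definition of analysis visit window") has one screening row and 22 post-baseline rows, from C1D8 (day 8) to C35D1 (day 715). It has no end-of-treatment row.

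The scan schedule is sparser. Protocol 10.1.12: "Echocardiography will be performed to assess the patient's LVEF every 12 weeks from the first dose of the investigational product". SAP 1.2.2.2.2 agrees: "Echocardiography is performed once every 12 weeks (and as clinically needed) from the first administration". Both documents also require an echocardiogram when study treatment stops, unless a result from the previous 4 weeks is available (Protocol 9.1.3.1; SAP 1.2.2.3.1).

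For reporting, SAP 5.6 says of the LVEF criteria: "The following will be summarized by treatment group at each visit and after treatment". The matching output in SAP 7 is "Table 14.3.5.1 Summary of LVEF abnormalities by visit-safety set", followed by a subject-level after-treatment summary, Table 14.3.5.2.

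**The concern.** A by-visit table is read down its rows as a profile over time on drug. That works only if each row rests on roughly the same kind of sample. Here some rows hold the routine 12-weekly scan of nearly everyone still on treatment. The rows between them hold whoever happened to be scanned: patients stopping treatment, patients scanned for a clinical reason, and patients whose routine scan was well off schedule. Proportions meeting the LVEF criteria in adjacent rows then describe different populations. A patient coming off drug also appears as an ordinary on-treatment visit. If the timing of, or reasons for, stopping differ between arms, so does the make-up of the in-between rows. LVEF is a named safety endpoint, and Table 14.3.5.1 is its only by-visit summary.

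**Working it through.** **Reproducing the SAP's windows.** SAP 2.2.6 sets each upper limit at the target day plus half the distance to the next target; each lower limit is the previous upper limit plus 1. Examples: C1D8, 8 + 7/2 = 11.5, cut to 11; C5D1, 85 + 21/2 = 95.5, cut to 95; C7D1, 127 + 42/2 = 148. All 22 pairs of limits reproduce exactly, assuming a further 42-day step after C35D1. Target spacings are 7, 21 and 42 days. The windows run from day 2 to day 736, which is 735 days.

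**Placing the scheduled scans.** With first dose on day 1, scans are due on day 1 + 84k, for k = 1 to 8.

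| Due day | Window | Limits | Days |
|---|---|---|---|
| 85 | C5D1 | 75–95 | 21 |
| 169 | C9D1 | 149–190 | 42 |
| 253 | C13D1 | 233–274 | 42 |
| 337 | C17D1 | 317–358 | 42 |
| 421 | C21D1 | 401–442 | 42 |
| 505 | C25D1 | 485–526 | 42 |
| 589 | C29D1 | 569–610 | 42 |
| 673 | C33D1 | 653–694 | 42 |

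That is 8 windows and 21 + 7 × 42 = 315 days. The other 14 are C1D8, C1D15, C2D1, C3D1, C4D1, C6D1, C7D1, C11D1, C15D1, C19D1, C23D1, C27D1, C31D1 and C35D1. They cover 735 − 315 = 420 days, or 420/735 = 57%.

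**Robustness.** The 8/14 split is unchanged if scans fall up to 7 days either side of the due day, or if week 12 is counted as day 84. Protocol 6.1 moves tumour assessments to every 4 cycles from C23 onward. If echocardiograms followed those visits (days 463, 547, 631 and 715), 5 + 4 = 9 windows would contain a planned scan and 13 would not.

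**When a routine scan changes row.** C5D1 (75–95) allows 10 days either side of day 85. C9D1 (149–190) allows 20 days early and 21 late, and the later scheduled windows do the same. A scan within 7 days of its due day always stays in the right row. A week-12 scan done on days 96 to 116 is reported as C6D1.

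**Where discontinuation scans land.** Take a patient scanned on time on day 169, and read 4 weeks as 28 days. A discontinuation scan is waived up to day 197 (169 + 28) and required from day 198 until the next routine scan on day 253. Of those 55 days (198–252), 35 (198–232) fall in C11D1 and 20 (233–252) in C13D1. So 35/55 = 64% of the days on which the scan is required fall in a row with no routine scan. This counts days, not patients; the documents give no counts of discontinuations by day.

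**The case against.** Four points can be made against this.

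First, SAP 2.2 item 3 confines statistical displays to planned visit points and leaves unplanned visits to the listings. Since LVEF is planned every 12 weeks, the in-between rows might simply not be printed. This helps only in part. The only list of scheduled days that SAP 2.2.6 ties to LVEF is Table 2.2.6-1 itself, with all 22 targets. Nothing says which of them are planned for LVEF, or whether a required discontinuation scan counts as planned.

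Second, displacement of routine scans is limited. This stands: it takes more than 10 days at week 12, or about three weeks later on. SAP 2.2.9 says that safety data are summarised by these windows during the epidemic, but no number of delayed echocardiograms is given.

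Third, the windows are the same in both arms of a double-blind trial, and no test or decision rests on the by-visit rows. This also stands, and it limits the severity.

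Fourth, a reader might infer that the 14 windows hold only for-cause or displaced scans, so that the table alternates between routine and symptom-triggered measurement and abnormality rates would jump from row to row. The documents do not support that. The discontinuation scan is required by protocol whatever the symptoms and can fall in any of the 14 windows. The documents also give no abnormality rates for routine or for-cause scans from which to size a jump.

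**Conclusion.** The mismatch is real and follows from the stated rules. Fourteen of the 22 post-baseline LVEF windows contain no scheduled 12-weekly scan (13 if late scans followed the C23, C27, C31 and C35 visits), and discontinuation scans are labelled as on-treatment visits. The affected rows of Table 14.3.5.1 cannot be read as on-schedule rates. That they will be small and selected is an inference from who can contribute to them, not a figure in the documents.

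The reach is narrow. On-time scans sit in the correct rows. Table 14.3.5.2 and the listing use all of a subject's data under rule 2 of SAP 2.2.6, and efficacy is untouched. The documents do not support a claim that the LVEF safety conclusion or the comparison of arms as a whole is distorted. Severity: minor, confined to one descriptive safety table.

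**What to change.** 1. Confirm whether echocardiograms after C21 stayed on the 12-weekly grid (days 505, 589, 673) or followed the C23, C27, C31 and C35 visits (days 463, 547, 631, 715). The documents do not settle this.
2. In SAP 2.2.6, add an LVEF-specific window table centred on the planned days: 85, 169, 253, 337, 421, then the confirmed later targets. On the 12-weekly grid, the SAP's half-distance rule gives upper limits of target + 42: 127, 211, 295, 379, 463, 547, 631 and 715. The last four are exactly the C23, C27, C31 and C35 days. If scans were done then, the later targets must move so that no boundary falls on a planned scan day. State the lower limit of the first window as well; by the existing table's convention it would otherwise start on day 2.
3. Restrict the by-visit rows of Table 14.3.5.1 to scheduled scans, because wider contiguous windows alone would still absorb the others. Show discontinuation scans in a separate end-of-treatment row. Leave for-cause scans to Table 14.3.5.2 and the listing.

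The cost is SAP wording and a second window table in programming, with no new data. The downside is that a scan can be up to about six weeks (42 days) from its nominal visit.

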### 2.2.7. Definition of baseline

Unless specifically indicated, the baseline values of the effectiveness endpoints of this study are defined as the last valid measurement of the endpoint before randomization. The baseline values of safety endpoints are defined as the last valid measurement before the first use of the investigational drug, including the day of medication.

Change from baseline will be calculated based on the measurement after baseline minus the measurement at baseline, or measurement after baseline - measurement at baseline.

### 2.2.8. Missing data processing

In general, missing values are not filled in unless specifically indicated.

#### 2.2.8.1. Main efficacy data

The primary endpoint of this study is the time outcome variable. When tumor efficacy assessment results are missing from a visit point, refer to [Table 4.1-2](#) and [Table 4.2-1](#) for the handling rules.

#### 2.2.8.2. Laboratory test values

If laboratory test values are recorded as lower than (and equal to) or higher than (and equal to) the test range values (for example,  $< x$ ,  $\leq x$ ,  $> x$ ,  $\geq x$ ), when summarizing descriptive statistics, this is handled based on the test range value (that is  $= x$ ). However, in data lists, the result recorded in the CRF will still be listed; that is, list " $< x$ ," " $\leq x$ ," " $> x$ ," or " $\geq x$ ."

#### 2.2.8.3. Partial missing dates

For missing dates of adverse events and past and concomitant medications or past and concomitant treatments (partially or completely missing), if not specifically indicated, judgment is made after filling in the missing dates in the following ways:

##### Missing start dates of adverse events

If only the "day" is missing from the start date of the adverse event, the rules for filling it in are as follows:

- 1) If the start date (month/year) of the adverse event is different from the date of first medication (month/year), fill in the first day of the month with the start date of the adverse event;
- 2) If the start date (month/year) of the adverse event is the same as the date of first medication (month/year) and is different from the date of outcome of the adverse event (month/year), fill in the "day" part of the date of first medication;

3) If the start date (month/year) of the adverse event is the same as the date of first medication (month/year) and is the same as the date of outcome (month/year) of the adverse event, fill in the “day” part of the date of first medication or the “day” part of the date of outcome of the adverse event, whichever is earlier.

If only the “month” and “day” are missing from the start date of the adverse event, fill in the earliest of the following dates:

- 1) The start date of the adverse event is January 1st of the year (if this date is not earlier than the date of first medication);
- 2) The “month” and “day” parts of the date of first medication (if the year of the start date of the adverse event is the same as the year of the date of first medication);
- 3) The last day of the year of the start date of the adverse event (if the year of the start date of the adverse event is earlier than the year of the first medication);
- 4) The date of outcome of the adverse event.

If the “year,” “month,” and “day” of the start date of the adverse event are all missing, do not fill them in.

#### **Missing dates of outcome of adverse events**

- 1) If only “date” of date of outcome of adverse event is missing, then fill in the last date of the month or the date of death (for deceased subjects), whichever is earlier
- 2) If both the “month” and “day” of the date of outcome of the adverse event are missing, fill in December 31 of the year or the date of death (for deceased subjects) as the “month” and “day” parts of the date of outcome of the adverse event, whichever is earlier;
- 3) If the “year,” “month,” and “day” of the date of outcome of the adverse event are all missing, do not fill them in

The start date of the adverse event (if missing, then the date after supplementation) is compared with the date of first medication to determine whether the adverse event is an adverse event that occurred during treatment.

#### **Missing start dates of past concomitant medications**

If the “year,” “month,” and “day” of the start date of the past concomitant medication are all missing, do not fill them in. If only the “day” is missing from the start date of the past and concomitant medication, the rules for filling it in are as follows:

- 1) If the start date (month/year) is different from the date of first medication (month/year), fill in the first day of the month of the start date
- 2) If the start date (month/year) is the same as the date of first medication (month/year) and different from the end date (month/year): If before the first medication (cmprior = “Y”), fill in the first day of the month; otherwise, fill in the “day” part of the date of first medication;
- 3) If the start date (month/year) is the same as the date of first medication (month/year) and the same as the end date (month/year): If before the first medication (cmprior = “Y”), fill in the first day of the month; otherwise, fill in the “day” part of the date of first medication or the “day” part of the end date, whichever is earlier.

If only the “month” and “day” are missing from the start date, fill in the earliest of the

following dates:

- 1) If the year of the start date differs from the year of the date of first medication, January 1 of the year of the start date;
- 2) If the year of the start date is the same as the year of the date of first medication: If before the first medication (cmprior = "Y"), then fill in January 1 of the year of the start date; otherwise, fill in the "month" and "day" parts of the date of first medication.

#### **Missing end dates of past and concomitant medications**

If the end date of past concomitant medication is missing, the rules for filling it in are as follows:

- 1) If only "day" is missing for the end date, fill in the last day of the month of the end date or the date of death (for deceased subjects) as the day part, whichever is earlier
- 2) If the "month" and "day" are both missing from the end date, fill in December 31 of the year of the end date or the date of death (for deceased subjects), whichever is earlier, as the "month" and "day" parts
- 3) If the "year," "month," and "day" of the end date are all missing, do not fill them in

#### **The start date of concomitant and subsequent anti-tumor treatment is missing**

If the "year," "month," and "day" of the start date of concomitant and subsequent anti-tumor [therapy] are all missing, do not fill them in.

If only the "day" is missing from the start date of concomitant and subsequent anti-tumor [therapy], the rules for filling it in are as follows:

- 1) If the start date (month/year) is different from the date of first medication (month/year), fill in the first day of the month of the start date
- 2) If the start date (month/year) is the same as the date of first medication (month/year) and different from the end date (month/year), fill in the "day" part of the date of first medication;
- 3) If the start date (month/year) is the same as the date of first medication (month/year) and the same as the end date (month/year), fill in the "day" part of the date of first medication or the "day" part of the end date, whichever is earlier.

If only the "month" and "day" are missing from the start date, fill in the earliest of the following dates:

- 1) 01/01 of the year of start date
- 2) If the year of the start date is the same as the year of the date of first medication, fill in the "month" and "day" parts of the date of first medication
- 3) If the year of the start date is earlier than the year of the date of this first medication, fill in December 31 of the year of the start date

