### Revision of History

As compared with Version 1.0 (Version 10/10/2020), the modified content in this V1.1 version is briefly described as follow

Page of original version	Brief description of modification
12	Estimating 25%, median, and 75% quantile of this indicator ➔ (changed to, the same below) Estimating 1/4 quantile, median and 3/4 quantile of this indicator
16	As “Date of adverse event outcome” was used in the study, some related description of “Missing start date of adverse event” is deleted.
17	Statement of “Missing start date of past concomitant medications” is modified: 1) 01/01 of the year of start date ➔ 1) If the year of start date is not that of initial medication, use 01/01 of the year of start date
18	The following statement in the section of “Missing end date of past and concomitant medications” is deleted, as it’s not filled in under such condition in 3): 4) If the year, month, and day are all missing and [the answer] to whether it is continuing is not “yes”, the start date serves as the end date. If the answer to whether it is continuing is “yes,” the data cutoff date serves as the end date
18	Expression approaches are unified: The rules for filling in concomitant and subsequent anti-tumor treatment ➔ Missing start date of concomitant and subsequent anti-tumor treatment 4) End date of concomitant and subsequent anti-tumor treatment ➔ Missing end date of concomitant and subsequent anti-tumor treatment
18	The date of death was missing when calculating the overall survival, rules for filling in “Missing date of death” are added
20	The conditions of subjects who terminated treatment for reasons other than disease progression after randomization are given in a list. ➔ The conditions of subjects who terminated treatment after enrolled and randomized are given in a list
21	The frequencies and percentages of past and concomitant medications are descriptively summarized by coded ATC3 category and treatment group. ➔ For past and concomitant medications, the frequencies and percentages of subjects by treatment group based on the coded ATC3 category and ATC1 category, ATC3 and preferred term are given separately.

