**The date of death is missing**

For subjects who are confirmed dead, if the complete date of death cannot be known, use the date of death after filling it in or the known last date of survival + 1, whichever is later, as the date of death. The rules for filling in the date of death are as follow:

- 1) If only the “day” is missing, fill in the 1st date of the month;
- 2) If “month” and “day” are missing, fill in January 1 of the year.

Other missing time data are not processed.

**Note:** In the data list, listing is still based on the original collected data.

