### **3.10. Concomitant and Subsequent Anti-Tumor Therapies**

The concomitant and subsequent anti-tumor therapies in this study will be coded with WHO Drug 2020Q1 or a higher version.

Concomitant anti-tumor therapies are other anti-tumor therapies used during medication with the investigational drug.

Subsequent anti-tumor therapies are other anti-tumor therapies used after the last use of the investigational drug.

The frequencies and percentages of concomitant and subsequent anti-tumor therapies are descriptively summarized by treatment group and coded ATC3 category.

The concomitant and subsequent anti-tumor therapies of all subjects are given in a list.

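### For anti-tumor therapy starts, the SAP's year-only fill is always 1 January, and no filled start of a subsequent therapy is bounded by last dose

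*SAP*

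**What the plan says.** SAP section 2.2.8.3 has a sub-rule for the start date of concomitant and subsequent anti-tumor treatment. When month and day "are missing from the start date, fill in the earliest of the following dates". Three candidates follow:

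1. "01/01 of the year of start date", with no condition;
2. the month and day of first dose, if the recorded year is the first-dose year;
3. 31 December of the recorded year, if that year is before the first-dose year.

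When only the day is missing, the fill is the first of the recorded month. If that month is the month of first dose, the fill is tied to the first-dose day instead. Last dose appears in neither part.

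SAP section 3.10 separates the two kinds of therapy by last dose: "Subsequent anti-tumor therapies are other anti-tumor therapies used after the last use of the investigational drug", and "Concomitant anti-tumor therapies are other anti-tumor therapies used during medication with the investigational drug".

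The scope sentence of 2.2.8.3 says that "judgment is made after filling in the missing dates in the following ways". It names past and concomitant treatments but not subsequent ones. The SAP does not say which derivations use the filled dates.

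**The concern.** A list resolved by taking the earliest date cannot work when its first entry is both unconditional and the earliest possible day of the recorded year. The neighboring rules suggest an oversight. For other medications, the V1.1 revision history replaces the same bare line with "If the year of start date is not that of initial medication, use 01/01 of the year of start date", and the current medication rule opens with "If the year of the start date differs from the year of the date of first medication". The adverse-event rule admits 1 January only when it does not precede first dose. The anti-tumor rule kept the bare line.

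The start of new anti-tumor therapy matters in three efficacy derivations, each only if filled dates are used:

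- **PFS.** The third row of Table 4.1-2 censors at the last valid scan before treatment termination or new systemic therapy. Where therapy start is the anchor, a fill that is too early moves censoring back.
- **DepOR.** SAP section 1.3.2 limits the best value to assessments before progression or before subsequent therapy. If that means whichever comes first, valid assessments can be cut.
- **ORR.** SAP section 4.4.1 stops counting responses from the time other therapy is used. On one literal reading, a response seen on study drug could be removed.

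**Working it through.** **1. Year-only rule.** Let Y be the recorded start year and F the first dose. Candidate 1 is 1 January of Y. Candidate 2 applies only if Y is the year of F; it equals F, which is on or after 1 January of Y. Candidate 3 applies only if Y is before the year of F; it is 31 December of Y. The minimum is always candidate 1.

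Enumeration over an assumed range: first doses from 1 November 2018 to 31 December 2020 give 61 + 365 + 366 = 792 dates. Crossed with start years 2016 to 2022, this is 792 × 7 = 5,544 combinations. The fill is 1 January in 5,544 of 5,544. Where Y is the first-dose year, the fill precedes first dose in 790 of 792; the other two are first doses on 1 January, where the dates tie. SAP section 1.2.4 starts treatment on the day of randomization, so these fills precede randomization too.

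**2. Illustrations (assumed dates).** First dose is 15 March 2019 in (a) and (b).

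- (a) Last dose 20 September 2019, start recorded as 2019: the fill is 1 January 2019, 73 days before first dose and 262 days before last dose.
- (b) Last dose 10 June 2020, start recorded as 2020: the fill is 1 January 2020, 161 days before last dose.
- (c) Last dose 10 June 2020, start recorded as June 2020: the fill is 1 June 2020, 9 days before last dose.

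**3. How often a subsequent start is filled on or before last dose.** Let L be last dose, g the gap in days (assumed; the documents give none), S = L + g the true start, and d the day of the month of S. With the day missing, the fill is S − (d − 1), which is on or before L when d − 1 ≥ g. Over 1,461 consecutive dates (48 months, 4 years):

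- day missing, g up to 28: share = 1 − 48g/1,461;
- year only: share = 1 − 4g/1,461.

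| Gap (days) | Day missing | Year only |
|---|---|---|
| 1 | 0.967 | 0.997 |
| 7 | 0.770 | 0.981 |
| 14 | 0.540 | 0.962 |
| 21 | 0.310 | 0.943 |
| 28 | 0.080 | 0.923 |
| 31 | 0 | 0.915 |

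These are shares per affected date, not per subject in the trial.

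**4. Third row of Table 4.1-2, day missing, no imaging progression.** If scans are uniformly placed every k days and therapy start is the anchor, the chance that the last scan lies between the fill and the true start averages mean(d − 1)/k. The mean of d − 1 over the 1,461 dates is 14.73.

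- 6-week scans: 14.73/42 = 0.351.
- 12-week scans (C23 onward): 14.73/84 = 0.175.

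If the earlier of termination and therapy start is the anchor, the loss is mean max(0, L − fill)/k. On 6-week scans this is 0.328, 0.206, 0.100, 0.031 and 0.002 at gaps of 1, 7, 14, 21 and 28 days, and half of each on 12-week scans. If termination is the anchor, the loss is zero.

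For a year-only start in the first-dose year, the fill precedes every post-baseline scan. With therapy start as the anchor, no on-study scan would remain before it.

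**5. Effect of a last-dose floor.** Filling with the later of the first day of the recorded period and L + 1 reduces the mean error (true start minus fill) from 14.7 to 5.3 days for a missing day at a 7-day gap. For a year-only date at a 14-day gap it falls from 182 to 12.8 days. No fill is then on or before last dose, by construction.

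**The case against.** Several objections stand and limit the point.

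- **Frequency.** Protocol section 9.1.3.4 and SAP section 1.2.2.3.4 collect details of subsequent therapy every 6 weeks, so the month will usually be known. Year-only dates should be uncommon.
- **Convention.** Filling with the first of the month is ordinary practice, and this SAP also uses it for adverse events, medications and death dates. The convention is not the fault; the missing last-dose bound is.
- **Scans.** Uniform placement is a simplification. Protocol section 9.1.3.1 requires a tumor evaluation at discontinuation unless one is available from the previous 4 weeks, which could raise or lower the loss. Which date anchors the third row is a separate ambiguity in Table 4.1-2.
- **Listings.** They keep the original dates, so a conflict can be seen. That does not correct the derived tables.

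A reader might also infer three stronger things that the documents do not support.

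- **Loss of PFS events or power.** The fourth row of Table 4.1-2 keeps imaging progressors as events, and the secondary censoring rules in Table 4.2-1 do not refer to new therapy.
- **Therapies moved from the subsequent to the concomitant table.** Section 3.10 defines the split by use during or after study drug and does not say that it is derived from filled dates.
- **Routine loss of on-drug responses.** Section 4.4.1 first requires that the other therapy be used after study drug was terminated. Read as a whole, the exclusion then begins after termination, in line with Protocol section 12.1.4.

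**Conclusion.** The rule is wrong as written, and the point is minor. Three parts follow from the text: the year-only fill is always 1 January; a same-year start is dated before first dose and randomization (except for a first dose on 1 January); and a therapy known to be subsequent can be dated on or before last dose, for year-only and day-missing starts alike.

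The effects on third-row censoring, DepOR and ORR are conditional on the filled dates being used, and on unresolved readings of those rules. The 35% and 17.5% are per affected case and rest on uniformly placed scans with therapy start as the anchor. The documents give neither the rate of partial dates nor the gap to next therapy, so the number of subjects affected is unknown; it is probably small.

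**What to change.** Amend the anti-tumor part of SAP section 2.2.8.3 as follows.

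1. Classify therapy as concomitant or subsequent from the collected record (form, follow-up period, unfilled date parts), not from filled dates. Step 2 needs this classification as its input.
2. For subsequent therapy, fill with the later of the first day of the recorded month or year and last dose of randomized study drug + 1. Keep the result within the recorded month or year and not after the therapy end date or death. The SAP already uses a later-of bound for death dates: "use the date of death after filling it in or the known last date of survival + 1, whichever is later".
3. For concomitant therapy begun on study, bound the fill below by first dose.
4. Delete options 2 and 3 of the year-only list, which can never be selected.
5. State that these filled dates are the ones used in the third-row PFS censoring, ORR and DepOR derivations.

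The cost is a few lines of SAP text and code, with no new data. SAP section 2.2 has the plan finalized before data lock, so the change belongs before then.
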